4.3 Participant and Study Status

Purpose:

To describe maternal and infant study status, including whether they are on study, and whether they are evaluable for analysis for both Cohort 1 and Cohort 2 infants, to summarize RAL adherence, and to summarize tolerability for Cohort 2 infants.

Analysis Program Validation:

Not required.

Data:

Mother and infant study status will be from PSTAT in CASE table. Reasons for off-study for mothers and infants will be from OFFST in F1601 CRF. Accrued and safety/PK evaluable infants information will be from STATUS, STUDMONR, COMENT tables and ADM0021 CRF. Duration of RAL while on study is from derived ARV dataset ARV2. Off-RAL reason will be from STATUS table (RSOFFRX from PE4005).

Analysis:

- a) Study Status of the Mothers and the Infants.
Table: Reasons for off-study for mothers
Table: Reasons for off-study for infants
- b) Treatment Status of the Infants.
Table: Reasons for off-treatment for infants
- c) Timing of 1st RAL Dosing for the Infants in Cohort 2
Table: Summary statistics for age (hours) for 1st RAL dosing for Cohort 2 infants
- d) Number of Infants Accrued and Evaluable for PK/Safety Analysis.

Table 3: Number of Cohort 1 Infants Accrued and Evaluable for PK/Safety Analysis (mock-up table)

	RAL-naive			RAL-exposed	Cohort Overall
	3mg/kg-3mg/kg	2mg/kg-3mg/kg	Overall	1.5mg/kg-3mg/kg	
Infants accrued	N	N	N	N	N
Infants evaluable for safety analysis^a	N	N	N(column %)	N(column%)	N(column %)
Infants evaluable for PK analysis^b	N	N	N(column %)	N(column%)	N(column %)

^a Based on if the patient received at least one dose of RAL

^b Based on team determination

Note: Similar table will be generated for Cohort 2 with appropriate column labels appropriate for Cohort 2 subgroups of infants.

- e) Reasons for analysis exclusions.

Table: Reasons for PK Analysis Exclusions

4.4 Data Completeness for Safety Data

Purpose:

To summarize data completeness according to the scheduled visits for infant safety data.

Analysis Program Validation:

Not required.

Data:

Infant observed visit data are from the following CRFs: LBW0093 (CHEMDT, CHEMOBT, HEMDT, HEMAObT) for hematologies and liver chemistries, PE6831 (VISITDT) for signs/symptoms and PE6852 (VISITDT) for diagnoses.

Analysis:

- a) Infant Safety Data Collection Schedule and Visit Windows for Cohort 1 and 2.
Wide analysis visit windows which include all study visits will be used to summarize data completeness. Upper limits for study visits weeks 6 and 24 will be used to define the safety endpoints for the primary and secondary safety objectives, respectively.

Table 4: Infant Safety Data Collection Schedule for Cohort 1

Evaluation	Scheduled visits							After 24 weeks ³
	Visits with windows specified in SoE	Entry (within 48 hrs of birth)	Day 3-4 of life	Dose 2 Day 7-10 of life ²	2 weeks of life (±2 days)	6 weeks of life (± 1 week)	24 weeks of life (± 4 weeks)	
	Wide analysis window	Days 1 and 2 of life	Days 3-6 of life	Days 7-11 of life	Days 12-22 of life	Days 23-49 of life	50-196 days of life	
Hematologies and liver chemistries (LBW0093)		X	X ¹	X	X	X	X	
Signs and Symptoms (PE6831)		X	X	X	X	X	X	
Diagnoses (PE6852)		X	X	X	X	X	X	

¹ Only total and direct bilirubin required.

² Pre-dose.

³ For safety evaluations done beyond the study specified follow-up for the neonates

Table 5: Infant Safety Data Collection Schedule for Cohort 2

Evaluation	Scheduled visits									
	Visits with windows specified in SoE	Entry (within 48 hrs of birth)	After second dose (2-4 days of life)	Day 6-9 of life	Day 15-18 of life	Day 28-32 of life	5-6 weeks of life	8-10 weeks of life (± 1 weeks)	24 weeks of life(± 4 weeks)	After 24 weeks ²
	Wide analysis window	Days 1 and 2 of life	Days 3-5 of life	Days 6-11 of life	Days 12-23 of life	Days 24-33 of life	Days 34-49 of life	Days 50-84 of life	≥85 days of life	≥197 days of life ²
Hematologies and liver chemistries (LBW0093)		X	X ¹	X	X	X	X	X	X	
Signs and Symptoms (PE6831)		X	X	X	X	X	X	X	X	
Diagnoses (PE6852)		X	X	X	X	X	X	X	X	

¹ Only total and direct bilirubin required.

² For safety evaluations done beyond the study specified follow-up for the neonates

b) Data Completeness Summaries of Infant Safety Data

Table: Frequency of infant expected and observed clinic visits with completed forms of IMPAACT P1097/P1110 Hematologies and Liver Chemistries (LBW0093), Signs/Symptoms (PE6831), and Diagnoses (PE6852).

4.5 RAL Adherence for Cohort 2 Infants

Purpose:

To summarize how compliant Cohort 2 infants were with study treatment. Adherence for Cohort 1 infants will be checked, but no summary table will be generated.

Analysis Program Validation:

Code review required.

Data:

Calculation of expected number of days on RAL will use data from the STATUS table (BIRTHDT, OFFSTDT and DOSE1DT). Calculation of actual number of days on RAL will use the data from TXW0276. Off-RAL reason will be from TXW0276 (RAL1RS AND RAL2RS).

Analysis:

Cohort 2 RAL adherence will be calculated using the following equation:

$$\% \text{ of days on RAL} = \frac{\text{actual number of days on RAL}}{\text{expected number of days on RAL}} \times 100\%$$

Note: “expected number of days on RAL” will consider the off-study date.

Table: Summary statistics of % of days on RAL.

Table: Summary of reasons of permanent discontinuation and temporary holds of RAL.

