5.1 Drug Regimens, Administration, and Duration

5.11 Regimen

Cohort 1: HIV-1 exposed full-term infants

For RAL-naïve (unexposed) infants: RAL 2 mg/kg oral granules for suspension as a single dose within 48 hours of birth in addition to standard of care ARV for PMTCT prophylaxis (refer to *Appendix III, Raltegravir Weight Band Dosing Table for Oral Granules for Suspension*).

For RAL-exposed infants: RAL 1.5 mg/kg oral granules for suspension as a single dose within 48 hours of birth in addition to standard of care ARV for PMTCT prophylaxis (refer to *Appendix III, Raltegravir Weight Band Dosing Table for Oral Granules for Suspension*).

For all Cohort 1 infants (RAL-naïve and RAL-exposed infants): Administer a second single dose of RAL 3 mg/kg oral granules for suspension in addition to standard of care ARV for PMTCT prophylaxis (refer to tables in Appendix III) on day 7 to 10 of life.

Cohort 2: HIV-1 exposed full-term infants

For RAL-naïve (unexposed) infants: RAL oral granules for suspension, provided as follows in addition to standard of care ARV for PMTCT prophylaxis (refer to tables in Appendix III): First Dose to be administered within 48 hours of life:

- 1.5 mg/kg once daily during Days 1-7 of life (week 1)
- 3.0 mg/kg twice daily during Days 8-28 of life (weeks 2-4)
- 6.0 mg/kg twice daily during Days 29-42 of life (weeks 5-6)

For RAL-exposed infants. First dose to be administered between 12 and 60 hours of life (refer to tables in Appendix III):

- 1.5 mg/kg once daily during Days 1-7 of life (week 1)
- 3.0 mg/kg twice daily during Days 8-28 of life (weeks 2-4)
- 6.0 mg/kg twice daily during Days 29-42 of life (weeks 5-6)

The reference weight to be used for each dose, and throughout the duration of that dose, is shown in the Table 10 below. The doses are calculated at 3 time points during the 6 weeks:

1. Initial dose based on birth weight;
2. At day 6-9 of life study visit; and
3. At day 28-32 of life study visit.

Note: Intent is to minimize the number of dose adjustments while receiving study treatment.

Table 10
Weight for Weight Bands (Cohort 2 RAL-exposed) in Appendix III

RAL dose regimen	Weight to be used for Appendix III weight bands
1.5 mg/kg once daily	Birth Weight Note: First dose administered between 12 and 60 hours of life
3.0 mg/kg twice daily	Weight on Day 6-9 of Life Study Visit (Note: if infant has lost weight during first week of life, use birth weight for dose calculation)

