5.32 Study Product Accountability

The site pharmacist is required to maintain complete records of all study products received from the NIAID CRPMC and subsequently dispensed. All unused study product must be returned to the NIAID CRPMC (or as otherwise directed by the sponsor) after the study is completed or terminated. The procedures to be followed are provided in the manual *Pharmacy Guidelines and Instructions for DAIDS Clinical Trials Networks* in the section Study Product Management Responsibilities.

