6.13 Bilirubin Management

Due to the potential for interactions between RAL and bilirubin affecting RAL pharmacokinetics and bilirubin elimination and toxicity (see Section 1.27) special management procedures for bilirubin will be used. Bilirubin concentrations and interventions to lower bilirubin (such as phototherapy and exchange transfusion) will be recorded but bilirubin will be graded according to the DAIDS Toxicity Table and

managed according to the schema described below. Hyperbilirubinemia will be managed by clinical caregivers according to local standards of care. If total bilirubin is >16.0 mg/dL or an exchange transfusion is performed, no further RAL doses will be administered but participants will continue to be followed for safety assessments. Participants who receive phototherapy may continue to receive study drug as long as total bilirubin concentration \leq 16.0 mg/dL.

The protocol team must be notified if study drug is held due to elevated bilirubin or of Grade 3 or 4 hyperbilirubinemia determined to be at least possibly related within 24 hours of site awareness at [contact].

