APPENDIX IV

DIAGRAM AND CAREGIVER INSTRUCTIONS FOR PREPARING AND ADMINISTERING RALTEGRAVIR ORAL GRANULES FOR SUSPENSION 10 mg/mL

IMPAACT P1110: Preparation and Dosing for Raltegravir (MK-0518) Granules in Foil Pouch

1. Fill cup with clean water
2. Use the 10 mL (large) syringe to measure 10 mL of water (markings on side of syringe)
3. Pour out remaining water from cup

Final study medicine concentration: 10 mg/mL

4. First, shake down powder to bottom of pouch. Then, open foil pouch and pour contents into cup
5. Add 10 mL water from the syringe back to the cup
6. Stir with spatula to mix study medicine evenly in water (mixture will be cloudy)

7. Insert syringe into cup and draw out study medicine
– *The correct size syringe and amount of study medicine will be told to you by your child's doctor*
8. Gently squirt medicine into child's mouth
9. Discard remaining medicine and clean supplies (refer to back of card).

Caregiver Instructions for Preparing and Administering RAL oral granules for suspension 10 mg/mL

Prepare raltegravir oral granules as follows:

1. Get one foil pouch containing the study medicine.
2. Using the mixing cup, fill approximately two-thirds full with room temperature (maximum 30° C), clean water (as defined by local standards).
3. Using the 10 mL large syringe and the markings on the side of the syringe as a guide, withdraw 10 mL of water from cup into syringe. Discard any remaining water from cup.
4. Shake down powder. Open the foil pouch of study medicine and pour the entire contents of pouch into mixing cup.
5. Add 10 mL of water from the large syringe back into the cup.
6. Stir with spatula until the study medicine and water are evenly mixed.
7. Using the dosing syringe withdraw the study medicine from the mixing cup; use the size syringe and amount of study medicine that the doctor has prescribed. Administer the study medicine into the baby's mouth. Use the markings on the side of syringe as a guide.

*Note: Once the study medicine is mixed with water, it should be given to the baby as soon as possible (ideally within 10 to 15 minutes) and no later than 1 hour after mixing with water. If the baby spits up most or all the dose in the first 30 minutes after administration, the dose should be repeated.

8. Throw away any remaining study medicine from the mixing cup in one of the following ways:

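### SAP 4.5 shortens the expected days on RAL only at the off-study date, so an infant stopped or held under the protocol scores as non-compliant

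*SAP*

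**What the plan says.** The stated aim of SAP 4.5 is "To summarize how compliant Cohort 2 infants were with study treatment". The measure is the percentage of days on RAL: actual days over expected days, times 100.

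- Numerator: "Calculation of actual number of days on RAL will use the data from TXW0276".
- Denominator: "Calculation of expected number of days on RAL will use data from the STATUS table (BIRTHDT, OFFSTDT and DOSE1DT". A note adds that it "will consider the off-study date". No treatment-stop or hold date is listed.
- Output: summary statistics of the percentage, and a separate table of reasons for permanent discontinuations and temporary holds.

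The protocol ends or interrupts RAL without ending follow-up in these places:

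- Section 6.13, for total bilirubin above 16.0 mg/dL or an exchange transfusion: "no further RAL doses will be administered but participants will continue to be followed for safety assessments".
- Section 6.12, Cohort 2: RAL is withheld for confirmed Grade 3 abnormalities and held for Grade 4, with stated exceptions. It is permanently discontinued for a confirmed drug-related Grade 4 reaction. Discontinued infants are asked to stay in follow-up to the 24-week visit.
- Section 4.11: if the mother's confirmatory HIV test is negative, dosing stops and safety follow-up continues.

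Section 5.11 gives RAL once daily on Days 1-7 and twice daily from Day 8 to Day 42; the middle step reads "3.0 mg/kg twice daily during Days 8-28 of life (weeks 2-4".

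**The concern.** A compliance measure should compare what was given with what the infant was supposed to be given. Once the protocol or the team has stopped RAL, nothing more is due. The SAP denominator nevertheless keeps running, because the infant is still on study. A directed stop then lowers the same percentage as missed doses would.

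SAP 4.3 names adherence and tolerability as separate things to summarize, and this ratio merges them. It is the only numerical adherence summary planned for a regimen that caregivers prepare and give at home. The RAL-exposed group has a minimum of 8 evaluable infants, so one early stop can visibly move its mean.

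The unit raises a second question. From Day 8 two doses are due each day, but the SAP does not say how a day with only one of them counts.

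**Working it through.** The plan gives a formula but no adherence figure, so there is nothing to reproduce. The check applies the formula to the protocol's regimen.

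**Inputs.** The planned end of dosing is Day 42, with 7 once-daily days and 35 twice-daily days (Protocol 5.11). The first dose falls on Day 1, 2 or 3, which is an assumption consistent with the 48-hour and 60-hour limits. SAP 4.5 does not write out the end of the expected period; I take it as Day 42 unless off-study comes first. Group sizes are 8 (Protocol 8.4) and 26 (SAP section 2). The stop days are illustrative.

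**Directed stop, infant still on study, every required dose given.** Score = days dosed / expected days. With the first dose on Day 1 there are 42 expected days:

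| Last day of RAL | SAP 4.5 score | Score if the denominator ends at the stop |
|---|---|---|
| Day 3 | 3/42 = 7.1% | 100% |
| Day 4 | 4/42 = 9.5% | 100% |
| Day 7 | 7/42 = 16.7% | 100% |
| Day 14 | 14/42 = 33.3% | 100% |
| Day 28 | 28/42 = 66.7% | 100% |
| Day 35 | 35/42 = 83.3% | 100% |

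The first-dose day changes little. Four dosing days score 4/41 = 9.8% from Day 2 and 4/40 = 10.0% from Day 3. A stop after Day 35 with the first dose on Day 3 scores 33/40 = 82.5%.

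**Directed hold of 7 days.** (42 - 7)/42 = 83.3%, against 100% if held days are removed.

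**Group mean, one infant stopped after Day 4, the others at 100%.**
- 8 infants: (7 x 100 + 9.5)/8 = 88.7%.
- 26 infants: (25 x 100 + 9.5)/26 = 96.5%.
- The median is 100% in both cases.

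**Undefined day on RAL.** A full course from Day 1 is 7 + 35 x 2 = 77 doses. An infant given one dose a day throughout receives 7 + 35 = 42 doses.
- By doses: 42/77 = 54.5%.
- If any dose makes a day on RAL: 42/42 = 100%.
- If only fully dosed days count: 7/42 = 16.7%.

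Neither day-based definition returns the dose-based figure, and the SAP does not choose between them.

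**The case against.** The strongest reply is that the information is not hidden and little depends on it. SAP 4.5 tabulates reasons for stops and holds, SAP 4.3 tabulates reasons for going off treatment, and SAP 4.6 plans a per-infant listing of antiretrovirals. The SAP calls the quantity a percentage of days on RAL and never attributes lost days to caregivers. As a share of planned days treated, it is a legitimate description. It enters neither the safety endpoints (SAP 4.6) nor the dose-finding guidelines (SAP 4.7). Pharmacokinetic sampling has its own check of the preceding 48 hours' dosing (Protocol 5.12), and infants with uncertain exposure are excluded from the pharmacokinetic analyses and replaced (Protocol 8.1).

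Most of this stands, and it limits the importance of the point. It does not remove it: the reasons tables disclose directed stops but leave the percentage uncorrected, and the section's stated purpose is compliance.

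A reader might go further and infer that half-dosed infants are scored as 100% adherent. That is not established. A day on RAL is undefined and the layout of TXW0276 is not shown; the score could equally be 16.7%. Nor do the documents say how often single doses are missed.

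A reader might also look to pouch counts for a dose-based measure, since Appendix IV begins each preparation with "Get one foil pouch containing the study medicine". Protocol 5.32 does say "All unused study product must be returned to the NIAID CRPMC (or as otherwise directed by the sponsor", but that is a pharmacy duty once the study is completed or terminated. It requires neither caregiver returns nor a count per infant.

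**Conclusion.** The denominator is wrong for its stated purpose. Following SAP 4.5 as written, a fully compliant infant whose RAL is stopped or held by direction scores below 100%, solely because follow-up continues. The shortfall is large for early stops (9.5% after 4 days), moderate for a 7-day hold (83.3%) and modest for late stops (about 83% after Day 35). It would therefore be too strong to say that every stopped infant appears grossly non-adherent. At group level, one 4-day stop costs about 11 percentage points of the mean among 8 infants and about 3.5 among 26, with the median unchanged.

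These sizes assume that the expected period otherwise ends at Day 42, that the infant stays on study past that day, and that the remaining infants score 100%. The documents do not predict how many directed stops will occur.

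The missing definition of a day on RAL is a secondary ambiguity. The whole point concerns a descriptive summary, but one that can be corrected easily.

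**What to change.** In SAP 4.5:

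1. End the expected period at the earliest of the planned end of dosing (Day 42), the off-study date and the date of a protocol- or team-directed permanent stop. Subtract days of directed hold. Use the TXW0276 treatment data and off-RAL reasons that the section already draws on.
2. Keep directed stops and holds in the existing reasons table. If the present ratio is still wanted, report it alongside as the percentage of planned days on treatment.
3. Define a day on RAL for the twice-daily period. Report doses given over doses prescribed only if the case report form holds dose-level data.

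The cost is SAP wording and a small programming change, with no new data for items 1 and 2. One check is needed first: the TXW0276 reason codes must separate directed stops and holds from caregiver decisions. Where they do not, the team would have to classify those few infants and document the rule used.

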4.6 Safety Analysis for SDAC Final Reports

Purpose:

To list the endpoints and tables of primary and secondary safety analyses for the SDAC final reports.

Analysis Program Validation:

Code review required. Primary analysis for primary safety endpoints will require double coding.

Data:

Infant safety data are adverse clinical and laboratory events reported on the following CRFs: Hematology and Liver Chemistries (LBW0093), Signs/Symptoms (PE6831), Diagnosis (PE6852) and Death (PE1414). (The following variables in the SDAC SAS datasets will be used: EVENTDSC, EVNGRDE, FORMNM and FORMTYP in EVENTS table; and TBILCV, BILPHOTO, BILTRANS, BILOTH and BILOTHSP in LBW0093).

Analysis:

There will be two final SDAC reports. The first report will focus on Cohort 1 (both RAL-naïve and exposed groups) and Cohort 2 RAL-naïve group. The second report will include Cohort 2 (both RAL-naïve and exposed groups). The safety analyses will include all infants who have had at least one dose of RAL. For Cohort 2, if there was dose adjustment after the interim analysis, a sensitivity analysis will be performed on infants who were enrolled after dose adjustment and only took the adjusted dose. Adverse Events (AEs) and Suspected Adverse Drug Reactions (SADRs) will exclude events classified by the team as “baseline” or “ongoing baseline” events.

- Safety endpoints for Cohorts 1 and 2 in SDAC final reports
 - Primary safety endpoint for the final analysis:
 - Adverse events of Grade 3 or 4 severity in the EVENTS table or death reported in the Death CRF with onset date at or after study entry through 6 weeks (i.e. through 49 days of age) of life
 - Secondary safety endpoints for the final analysis:
 - Adverse events of Grade 3 or 4 severity in the EVENTS table or death reported in the Death CRF with onset date at or after study entry through 24 weeks of life (through 196 days of age)
 - Suspected adverse drug reaction (SADR*) of Grade 3 or 4 severity or death with onset date at or after study entry through 6 weeks (through 49 days of age) of life
 - Suspected adverse drug reaction (SADR*) of Grade 3 or 4 severity or death with onset date at or after study entry through 24 weeks of life (i.e. through 196 days of age)

* For the SDAC final report, SADRs will include the following attribution to drug: 11 – “Definitely related”; 12 – “Probably related”; and 13 – “Possibly related”.

- Summary tables for Cohorts 1 and 2 in the SDAC final reports (Analysis for primary and

secondary safety endpoints for final analysis)

Note: Summary tables will include statistics for infant subgroups and overall and listing will include information on infant in utero RAL exposure and RAL dosing.

Table: Summary tables showing number (%) and the 2-sided 90% confidence interval (CI) using the Clopper-Pearson exact method estimates of the proportion of infants meeting the primary and secondary safety endpoints(will provide as footnote number of infants with missing data). The primary analysis will be on the primary safety endpoint.

Table 6: Proportion of Infants Meeting the Primary Safety Endpoint (mock-up table)

RAL-naïve			RAL-exposed	Overall
3mg/kg-3mg/kg	2mg/kg- 3mg/kg	Overall	1.5mg/kg-3mg/kg	
N (%) [90% CI]	N (%) [90% CI]	N (%) [90% CI]	N (%) [90% CI]	N (%) [90% CI]

Note: Similar table will be generated for Cohort 2 with appropriate column labels appropriate for Cohort 2 subgroups of infants.

Table: Summary tables of worst adverse events (laboratory, signs/symptoms and diagnoses) for each of the primary and secondary safety endpoint.

Table: Summary of worst grade baseline events (laboratory, signs/symptoms and diagnoses).

Table: Listing of reasons for infant death and age (weeks) at death.

Table: Summary table showing number (%) and the 2-sided 90% confidence interval (CI) using the Clopper-Pearson exact method estimates of the proportion of infants who had total bilirubin exceeding 16.0 mg/dL, or received phototherapy, transfusion therapy or other therapies for hyperbilirubinemia.

The following SDAC internal listings will be generated to facilitate the write-up of the SDAC final report. The listings will also be provided to the manuscript writing team. SDAC public IDs will be used and no identifying dates will be provided.

- a. Per infant listings of baseline events, AEs and SADRs with site and team assessment of drug attribution.
- b. Per infant listing of ARVs from TXW0276 and PE0421.

